6.5.5.2 AE Reporting Requirements

The investigators on this protocol will report any suspected adverse events that occur after [¹⁸F]fluciclovine administration and within the specified follow-up period to [name] and they will work together to determine whether there was an adverse event or adverse reaction and the severity of the adverse event or reaction.

All AEs will be followed by the investigators until resolution, stabilization, scientifically and clinically satisfactory explanation as to attribution and etiology is achieved, or until subject is lost to follow up.

6.5.5.3 CAEPR/ASAE for [¹⁸F]Fluciclovine

The Comprehensive Adverse Event and Potential Risks list (CAEPR) provides a single list of reported and/or potential adverse events (AE) associated with an agent using a uniform presentation of events by body system. The Agent Specific Adverse Event List (ASAEL) would include the expected adverse events associated with the use of [¹⁸F]fluciclovine. At this time, there have been rare reported AEs associated with the use of a [¹⁸F]fluciclovine in clinical studies ($\leq 1\%$ of patients). The most common adverse reactions were injection site pain, injection site erythema, and dysgeusia. We will continue to update our CAEPR and ASAE lists as this study progresses, including by reviewing the literature and our in-house data safety monitoring. If any are found, we will begin an ASAE list. Any information on reported AEs for [¹⁸F]fluciclovine will be provided by the sponsor to all of the investigators on this protocol.

6.5.5.4 Potential but Unexpected AE for [¹⁸F]Fluciclovine

There have been rare reported AEs associated with the use of a [¹⁸F]fluciclovine in clinical studies ($\leq 1\%$ of patients). The most common adverse reactions were injection site pain, injection site erythema, and dysgeusia.

Other general risks for PET/MRI imaging include:

- The injection site may become infected.
- The dose might be extravasated into tissues surrounding the vein catheter leading to localized pain/discomfort.

Radiation risks: [¹⁸F]fluciclovine injection contributes to lifetime radiation accumulation. The smallest dosage for imaging and safe handling are used for these protocols. The organ and total body doses associated with [¹⁸F]fluciclovine imaging are comparable to those associated with other widely used clinical nuclear medicine procedures.

6.5.5.5 Review of Safety Information

As required by 21 CFR 312.32(b), the physician investigators will promptly review all information relevant to the safety of the drug. The physician investigators will also be providing much of this information to the local IRB as well for data safety and review monitoring. The review will include determining whether there is a safety event over time and the causality. Reporting will be as described in Table 1.

Characterization of the severity of an Adverse Event: Adverse events will be graded as below.

Grade: Grade denotes the severity of the AE. An AE is graded using the following categories:

- Mild
- Moderate
- Severe
- Life-threatening or disabling
- Fatal

NOTE: Severity is graded on the Cancer Therapy Evaluation Program (CTEP) Common Terminology Criteria for Adverse Events (CTCAE) based scale for each adverse event. For example, an abnormal hemoglobin value is graded for severity from 1 to 5 [death] based upon where that value falls on the CTCAE scale of abnormal hemoglobin values.

“Severity” is NOT the same as “Seriousness.” All appropriate clinical areas should have access to a copy of the most current CTCAE and a copy of the CTCAE can be downloaded from (<http://ctep.cancer.gov>).

Attribution of cause: The physician investigators will determine whether an adverse event was related to a medical treatment or procedure.

Definitions taken from our work with CTEP and NIH give the following definitions for “Attribution” that we will adopt for this IND study:

Attribution is a clinical determination, by the investigator, as to whether an AE is related to a medical treatment or procedure. Attribution categories are:

- **Definite:** The AE is **clearly related** to a treatment or procedure
- **Probable:** The AE is **likely related** to a treatment or procedure
- **Possible:** The AE **may be related** to a treatment or procedure
- **Unlikely:** The AE is **likely unrelated** to a treatment or procedure
- **Unrelated:** The AE is **clearly not related** to a treatment or procedure
- **NOTE:** Attribution is part of the assessment of an adverse event. Determining that an event is ‘unlikely related’ or ‘unrelated’ to a study agent or procedure does NOT make the event unreportable, or disqualify the event as an AE. As defined above, an AE is reportable as specified herein if it occurred: **“during the Adverse Event reporting period defined in the protocol**, or by applicable guidance, regulation, or policy.”

6.5.5.6 Adverse Event Reporting

Expedited AE reporting for this study will be done through the Cancer Consortium, IRB and FDA and as required by FDA MedWatch. These requirements are briefly outlined in the table below.

Table 1. Reporting Requirements.

	Unexpected		Expected
	Adverse Reaction (known or suspected attributable to the use of	AE not attributable to	AE, AR

	[¹⁸ F]Fluciclovine	[¹⁸ F]Fluciclovine	
	Serious including life-threatening (or death)	Nonserious	Life-Threatening or serious or not serious
Reporting Time Requirement to the FDA	Report to FDA ASAP and within 7 days of discovery of event	Annual Continuation Review submission	Annual Continuation Review submission
Reporting Form for the FDA	IND Safety report of potentially serious risk	Annual Reports / Case reports	Annual Reports / Case reports
Reporting Time Requirement to the local IRB	Report to IRB ASAP within 10 days of discovery of event (suspected is defined as 50% probability attributable to [¹⁸ F]Fluciclovine study) this also includes any increased risks with the study even without an AE	At continuation review time	At continuation review time
Reporting form for the IRB	Expedited Reporting Form for Unanticipated Problems or Noncompliance and Adverse Event Reporting Form	Form for Unanticipated Problems or Noncompliance, Case reports on continuation form, Data Safety Monitoring Reports	Form for Unanticipated Problems or Noncompliance, Case reports on continuation form, Data Safety Monitoring Reports

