6.5.5.1 General Definitions (from 21 CFR 312.32 (a))

Adverse Event (AE): An Adverse Event is an untoward medical occurrence associated with the use of the drug in humans, whether or not considered drug related. For this study, the drug is [¹⁸F]fluciclovine and adverse events would include any events experienced by a study participant during the Adverse Event reporting period defined in Table 1 whether or not it was considered to be related to the [¹⁸F]fluciclovine. At the conclusion of the imaging study, the imaging technologist will observe the patient and also inquire if they are back to their usual state of health. If a negative answer is received, then the physician will be called to investigate this report as a possible adverse reaction.

Adverse Reaction: An Adverse Reaction is any adverse event caused by a drug. In this study, the drug is [¹⁸F]fluciclovine.

Suspected adverse reaction means any adverse event for which there is a reasonable possibility that the IND drug caused the adverse event. For the purposes of IND safety reporting, “reasonable possibility” means there is evidence to suggest a causal relationship between the drug and the adverse event. A suspected adverse reaction implies a lesser degree of certainty about causality than adverse reaction, which means any adverse event caused by a drug.

An adverse event or suspected adverse reaction is considered “unexpected” if it is not listed in the investigator brochure or is not listed at the specificity or severity that has been observed; or, if an investigator brochure is not required or available, is not consistent with the risk information described in the general investigational plan or elsewhere in the current application.

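### The local IRB row of Table 1 defines a suspected reaction as 50% probability, in conflict with the reasonable-possibility definition in 6.5.5.1, so some serious unexpected events could miss the 10-day IRB report

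*Combined protocol and SAP*

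**What the plan says.** Three parts of the protocol's safety section bear on when a reaction counts as suspected.

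- **Section 6.5.5.1, General Definitions.** "Suspected adverse reaction means any adverse event for which there is a reasonable possibility that the IND drug caused the adverse event". For IND safety reporting, it adds that reasonable possibility "means there is evidence to suggest a causal relationship between the drug and the adverse event". It also says: "A suspected adverse reaction implies a lesser degree of certainty about causality than adverse reaction". No probability is given.
- **Section 6.5.5.5, Review of Safety Information.** "Reporting will be as described in Table 1". The section also adopts five attribution categories. Two matter here: Possible ("The AE may be related to a treatment or procedure") and Probable ("The AE is likely related to a treatment or procedure"). None of the five is given a probability or linked to the term suspected.
- **Section 6.5.5.6, Table 1.** For serious, unexpected reactions known or suspected to be due to fluciclovine, the local IRB row says "Report to IRB ASAP within 10 days of discovery of event". A parenthesis in the same cell adds: "suspected is defined as 50% probability attributable to" fluciclovine. The other IRB timing cells defer to continuation review. The FDA cell in the same column sets a 7-day limit and does not define suspected.

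**The concern.** One word decides whether the IRB hears of a serious, unexpected event within days or at a periodic review, and the protocol gives that word two meanings. The definitions section asks only for evidence pointing to a causal link. The table asks for even odds. An event can satisfy the first and fall short of the second.

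An investigator who works from the table, as 6.5.5.5 directs, may hold back an event that the definitions section calls suspected. At stake is timely IRB oversight. The reactions that 6.5.5.3 names as most common are injection site pain, injection site erythema and dysgeusia. A serious systemic event would therefore probably count as unexpected, and the meaning of suspected would then settle how quickly it is reported.

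**Working it through.** The 50% is a stipulated definition, not a figure derived from other inputs, so there is nothing to reproduce. The check is a comparison of texts followed by a routing test.

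**Step 1: the two definitions.**

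| | Section 6.5.5.1 | Table 1, local IRB row |
|---|---|---|
| Test | Reasonable possibility, meaning evidence that suggests causality | 50% probability |
| Numeric threshold | None | 50%, with no inequality sign |
| Link to the attribution categories in 6.5.5.5 | None | None |

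**Step 2: routing.** Take an event that is serious and unexpected and has some evidence of a causal link. Let p be the investigator's probability that fluciclovine caused it.

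- p above 50%: suspected under both definitions, so the 10-day IRB report applies.
- p equal to 50%: suspected under 6.5.5.1. Under Table 1 the answer depends on whether the missing sign is 'at least' or 'more than'.
- p below 50% (illustrative range: above 0% to just under 50%): suspected under 6.5.5.1 but not under the IRB row. Read literally, the event falls outside the only cell that carries the 10-day limit.
- FDA row, same event: no 50% wording appears. If 6.5.5.1 is applied there, the 7-day FDA report still follows.

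Nonserious and expected events are not expedited under either definition, so they are unaffected.

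**Step 3: other routes to the IRB.**

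- Section 6.5.5 says adverse events also go to the IRB under the IRB's own requirements. It mentions SAE reporting to the IRB as well. It gives no timing or causality threshold, and the IRB's requirements are not in the documents.
- Section 6.5.5.7 sends reports of life-threatening adverse reactions to the IRB but sets no IRB deadline. Section 6.5.5.1 reserves 'adverse reaction' for events the drug caused, so a merely suspected event is not clearly included. Serious events that are not life-threatening are outside this clause.
- The same Table 1 cell also brings in any increase in study risk. That could catch some events, but it does not say which meaning of suspected applies.

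**Step 4: how many events.** Enrolment is 15 (6.2), with two scans each (4.6.2), so injections number at most 15 × 2 = 30. Section 6.5.5.3 puts tracer-associated events at no more than 1% of patients. At that ceiling, 0.01 × 15 = 0.15 patients are expected to have any such event, or 0.01 × 30 = 0.3 if the rate is applied to each injection. Serious, unexpected events judged below 50% would be a fraction of these. The figures are only a guide, because a coincidental event in this population could also be judged possibly related.

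**The case against.** The best defence is that a separate local IRB convention may be intended. Section 6.5.5.1 ties its explanation of reasonable possibility to IND safety reporting, and the Table 1 wording refers to the fluciclovine study rather than to the drug alone. This is plausible. But the protocol does not say so, and it uses the same word for both tests.

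A second defence is that other clauses reach the IRB and that 6.5.5.6 calls the table a brief outline. This stands in part: it cannot be shown that any given event would be missed. It does not remove the conflict, since none of those clauses gives both a deadline and a causality threshold for a suspected event that is not life-threatening. Reporting of every SAE to the manufacturer within 24 hours means that events are captured, but it does not put them before the IRB.

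Third, the column headings of Table 1 are split in the readable text, so the cell in which a below-50% event would land is not certain. That is fair. What can be said is that such an event does not meet the literal condition of the 10-day cell, and that the other IRB timing cells all point to continuation review.

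Two stronger readings are tempting and are not supported:

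- A reader might infer that FDA reporting is compromised too, because one column heading serves both rows. The 50% parenthesis sits only in the IRB cell, and 6.5.5.1 already supplies the definition for IND reporting.
- A reader might infer that every event rated Possible is excluded. Section 6.5.5.5 attaches no probability to that category, so equating it with below 50% is an inference.

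**Conclusion.** The conflict is real and confined to the local IRB row of Table 1. It is a stated rule that contradicts the protocol's own definition, not a missing detail. A serious, unexpected event with evidence of causality but a judged probability below 50% could miss the 10-day IRB report, most clearly when it is not life-threatening.

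The expected number of affected events is small: fewer than one on the protocol's own 1% figure. The point should be corrected because it concerns participant safety oversight and is cheap to fix.

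The conclusion assumes that staff follow Table 1 literally, as 6.5.5.5 directs, and that the IRB's unseen requirements do not already settle the matter.

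**What to change.** Reconcile 6.5.5.1, 6.5.5.5 and Table 1 in 6.5.5.6:

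1. In the local IRB row, replace the 50% parenthesis with a reference to the 6.5.5.1 definition.
2. State in 6.5.5.5 which of the five attribution categories count as suspected for expedited reporting.
3. If the local IRB does require a 50% convention, keep it as an IRB-only term under a different word and state whether 50% itself qualifies.

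The cost is one table phrase, a linking sentence in 6.5.5.5 and, at most, a rare additional expedited report in 15 men. No endpoint, sample size or analysis changes.

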6.5.5.7 Expedited Adverse Reaction Reporting Guidelines

Life-threatening (or fatal) adverse reactions must be reported within 7 days to the FDA. The FDA should be notified as soon as the adverse reaction is discovered by telephone or fax or email. The instructions and forms are available at <http://www.fda.gov/Safety/MedWatch/HowToReport/default.htm> The report should be sent ASAP by mail and followed with a follow-up report. Individual IND safety reports to FDA are submitted on the Medwatch FDA Form 3500A as an “IND Safety Report”. The form should be sent to The Director, Office of Generic Drugs in the Center for Drug Evaluation

and Research at FDA. The address and phone numbers are available at: <http://www.fda.gov/AboutFDA/CentersOffices/CDER/ucm119100.htm>.

All life threatening adverse reactions reports are submitted to the FDA, THE UAB IRB and to all investigators. A copy of the report is kept on file.

6.5.6 Protection of Privacy

Patients will be informed of the extent to which their confidential health information generated from this study may be used for research purposes. Following this discussion, they will be asked to sign the HIPAA form and informed consent documents. The original signed document will become part of the patient's medical records, and each patient will receive a copy of the signed document. The use and disclosure of protected health information will be limited to the individuals described in the informed consent document.

6.6 Data Management

All patient data will be anonymized and stored on encrypted password-protected computers with access only given to members of the research team. Standard precautions regarding HIPAA will be taken to avoid any breach in patient privacy.

